## Appendix 4: Tables for Clinical and Laboratory Abnormalities

The tables for clinical and laboratory abnormalities are presented in Tables A and B, respectively, according to the FDA Guidance for Industry: *Toxicity Grading Scale for Healthy Adult and Adolescent Volunteers Enrolled in Preventive Vaccine Clinical Trials (September 2007)*.

### A. Tables for Clinical Abnormalities

Local Reaction to Injectable Product	Mild (Grade 1)	Moderate (Grade 2)	Severe (Grade 3)	Potentially Life Threatening (Grade 4)
Pain	Does not interfere with activity	Repeated use of non-narcotic pain reliever >24 hours or interferes with activity	Any use of narcotic pain reliever or prevents daily activity	Emergency room visit or hospitalization
Tenderness	Mild discomfort to touch	Discomfort with movement	Significant discomfort at rest	Emergency room visit or hospitalization
Erythema/redness a	2.5-5 cm	5.1-10 cm	>10 cm	Necrosis or exfoliative dermatitis
Induration or swelling b	2.5-5 cm and does not interfere with activity	5.1-10 cm or interferes with activity	>10 cm or prevents daily activity	Necrosis

a In addition to grading the measured local reaction at the greatest single diameter, the measurement should be recorded as a continuous variable.

b Induration (underlying hardening of tissue associated with inflammation) or swelling (localized tissue distension) should be evaluated and graded using the functional scale as well as the actual measurement.

Vital Signs a	Mild (Grade 1)	Moderate (Grade 2)	Severe (Grade 3)	Potentially Life Threatening (Grade 4)
Fever (°C) b (°F) b	38.0-38.4 100.4-101.1	38.5-38.9 101.2-102.0	39.0-40 102.1-104	>40 >104
Tachycardia – beats per minute (12-17 years)	101-115	116-130	>130	ER visit or hospitalization for arrhythmia
Tachycardia – beats per minute (5-11 years)	115-125	126-140	>140	ER visit or hospitalization for arrhythmia
Bradycardia – beats per minute c (12-17 years)	50-54	45-49	<45	ER visit or hospitalization for arrhythmia
Bradycardia – beats per minute d (5-11 years)	67-74	52-66	<52	ER visit or hospitalization for arrhythmia
Hypertension (systolic) – mm Hg (12-17 years)	141-150	151-155	>155	ER visit or hospitalization for malignant hypertension
Hypertension (systolic) – mm Hg (5-11 years)	120-129	130-139	>140	ER visit or hospitalization for malignant hypertension
Hypertension (diastolic) – mm Hg (12-17 years)	91-95	96-100	>100	ER visit or hospitalization for malignant hypertension

Vital Signs a	Mild (Grade 1)	Moderate (Grade 2)	Severe (Grade 3)	Potentially Life Threatening (Grade 4)
Hypertension (diastolic) – mm Hg (5-11 years)	80-84	85-89	>90	ER visit or hospitalization for malignant hypertension
Hypotension (systolic) – mm Hg (12-17 years)	85-89	80-84	<80	ER visit or hospitalization for hypotensive shock
Hypotension (systolic) – mm Hg (5-11 years)	<70 without symptoms	<70 with symptoms	<70 requiring medications or fluids	ER visit or hospitalization for hypotensive shock
Respiratory rate – breaths per minute (12-17 years)	17-20	21-25	>25	Intubation
Respiratory rate – breaths per minute (5-11 years)	22-24	25-27	>27	Intubation

ER = emergency room

a Subject should be at rest for all vital sign measurements.

b Oral temperature; no recent hot or cold beverages or smoking.

c Heart rate should be measured while the subjects is awake. BPM based on resting heart rate between 60 to 100 beats per minute for adolescents. Use clinical judgment when characterizing bradycardia among some healthy subject populations, for example, conditioned athletes.

Systemic (General)	Mild (Grade 1)	Moderate (Grade 2)	Severe (Grade 3)	Potentially Life Threatening (Grade 4)
Nausea/vomiting	No interference with activity or 1-2 episodes/24 hours	Some interference with activity or >2 episodes/24 hours	Prevents daily activity, requires outpatient IV hydration	ER visit or hospitalization for hypotensive shock
Diarrhea	2-3 loose stools or <400 g/24 hours	4-5 stools or 400-800 g/24 hours	6 or more watery stools or >800 g/24 hours or requires outpatient IV hydration	ER visit or hospitalization
Headache	No interference with activity	Repeated use of non-narcotic pain reliever >24 hours or some interference with activity	Significant; any use of narcotic pain reliever or prevents daily activity	ER visit or hospitalization
Fatigue	No interference with activity	Some interference with activity	Significant; prevents daily activity	ER visit or hospitalization
Myalgia	No interference with activity	Some interference with activity	Significant; prevents daily activity	ER visit or hospitalization
Illness or clinical adverse event (as defined according to applicable regulations)	No interference with activity	Some interference with activity not requiring medical intervention	Prevents daily activity and requires medical intervention	ER visit or hospitalization

ER = emergency room; IV = intravenous

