### **12.5. Study Stopping Rules**

Study enrollment will be suspended and vaccinations will be put on hold pending DSMB expedited review of all pertinent data in the event of any one of the following:

1. One Grade 4 or higher AE that is at least possibly related to the vaccine

2. Five participants in the first 100 HA/MCD participants vaccinated or 5% of HA/MCD participants thereafter experience a Grade 3 systemic allergic reaction at least possibly related to the vaccine

Following their unblinded review, the DSMB will determine whether modifications should be made to study conduct and whether and when enrollment and vaccinations can resume.

The study may be suspended or terminated by DAIT/NIAID or the DSMB upon review of any observations, events, or new information that merits such action. In the case of suspension or premature termination, DAIT/NIAID will promptly inform the investigators and regulatory authorities as appropriate of the suspension or termination and the reason for suspension/termination.

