### 13.2. Definitions

#### 13.2.1. Adverse Event (AE)

An AE is any untoward medical occurrence associated with the use of an intervention in humans, whether or not considered intervention-related (21 CFR 312.32(a)).[19]

The investigator must report adverse events regardless of relationship to study therapy regimen or study mandated procedures.

For this study, an adverse event will include the following associated with the vaccinations/placebo administration or procedures:

- **Vaccine or placebo administration:**
  - All AEs occurring after vaccination/placebo administration and within 7 days after the last dose of vaccine or placebo
  - All solicited local reactions, with the exception of injection site reactions of erythema/redness and induration/swelling measuring <2.5 cm, will be reported as AEs.

- **Study mandated procedures:**

Events related to the following procedures will be considered AEs, with the exception of:

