**13.2.2. Solicited and Unsolicited Adverse Events**

For the purposes of this study, the following specific local and systemic reactogenicity events, as well as symptoms of a potential allergic reaction, will be solicited from the participant for 7 days post-vaccination, inclusive of the vaccination/placebo administration day. Refer to [Section 8.2 Enrollment Visit \(Day 1\)](#) and [Section 9.2 Enrollment Visit \(Day 1\)](#).

- Solicited local reactions at the injection site will include erythema/redness, swelling/induration (hardness), and pain.
- Solicited systemic reactions will include fever (assessed as daily oral temperature), myalgia, arthralgia, fatigue, headache, nausea, vomiting, diarrhea, and chills.
- Solicited symptoms related to a potential allergic reaction will include the following:
  - Skin: hives, swelling other than injection site, itching, redness other than injection site, rash
  - Respiratory: wheezing, shortness of breath, coughing, tightness in the throat or chest, sneezing, nasal stuffiness or congestion
  - Gastrointestinal: trouble swallowing, abdominal cramps, diarrhea, nausea, vomiting
  - Dizziness or lightheadedness

All other AEs reported by the participant during the study will be defined as unsolicited AEs.

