### 13.3. Grading and Attribution of Adverse Events

#### 13.3.1. Grading Criteria

##### 13.3.1.1. Grading of Adverse Events Other than Systemic Allergic Reactions

The study sites will grade the severity of non-allergic adverse events experienced by the study participants according to the criteria set forth in the FDA Guidance for Industry Toxicity Grading Scale for Healthy Adult and Adolescent Volunteers Enrolled in Preventive Vaccine Clinical Trials (September 2007); hereafter, referred to as the FDA Toxicity Grading Scale.

Adverse events will be graded on a scale from 1 to 5 according to the following standards in the FDA Toxicity Grading Scale ([Appendix 4: Tables for Clinical and Laboratory Abnormalities](#)):

- Grade 1 = Mild
- Grade 2 = Moderate
- Grade 3 = Severe
- Grade 4 = Life-threatening
- Grade 5 = Death

Events grade 1 or higher will be recorded on the appropriate AE eCRF for this study.

For grading an abnormal value or result of a clinical or laboratory evaluation (including, but not limited to, a radiograph, an ultrasound, an electrocardiogram etc.), a treatment-emergent adverse event is defined as an increase in grade from baseline or from the last post-baseline value that doesn't meet grading criteria. Changes in grade from screening to administration of the first dose of vaccine/placebo will also be recorded as adverse events, but are not treatment-emergent. If a specific event or result from a given clinical or laboratory evaluation is not included in the FDA Toxicity Grading Scale, then an abnormal result would be considered an adverse event if changes in therapy or monitoring are implemented as a result of the event/result.

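### Section 13.2.1 exempts injection-site swelling under 2.5 cm from AE reporting by size alone, although Appendix 4 gives such a swelling Grade 2 or 3 when it limits activity

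*Protocol*

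**What the plan says.** Three places in the protocol bear on this.

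- **Section 13.2.1 (what counts as an AE).** All solicited local reactions, "with the exception of injection site reactions of erythema/redness and induration/swelling measuring <2.5 cm, will be reported as AEs". Swelling falls under this sentence because Section 13.2.2 lists it: "Solicited local reactions at the injection site will include erythema/redness, swelling/induration (hardness), and pain".
- **Appendix 4, table of clinical abnormalities (how swelling is graded).** Grade 1 is "2.5-5 cm and does not interfere with activity". Grade 2 is "5.1-10 cm or interferes with activity". Grade 3 is ">10 cm or prevents daily activity". Note b adds that induration or swelling "should be evaluated and graded using the functional scale as well as the actual measurement".
- **Section 13.3.1.1 (what is recorded).** It applies the Appendix 4 scale and states: "Events grade 1 or higher will be recorded on the appropriate AE eCRF for this study".

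SAP Section 8.2 takes over the same FDA toxicity scale for the severity of non-allergic AEs. It does not mention the 2.5 cm exemption.

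**The concern.** The exemption looks at diameter only, while the grading scale looks at diameter and function. The two rules part company for a swelling that is small but limits what the participant can do. Appendix 4 calls it moderate or severe, and Section 13.2.1 takes it out of AE reporting.

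What is at stake is the completeness of the local-reaction data. The severity summaries and the between-arm Fisher tests in SAP Section 8.2 are built on AEs. The minimum safety listing for the DSMB (Protocol Section 13.8.2.1, SAP Section 10) covers reported AEs and SAEs. A reaction that never reaches the AE form appears in none of these. Any such omission can only lower the number or the grade of local reactions shown.

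**Working it through.** No arithmetic applies, and the plan states no figure to reproduce. The check sets the three rules side by side for a solicited swelling of less than 2.5 cm at each functional level.

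| Swelling under 2.5 cm | Appendix 4 | Section 13.2.1 | Section 13.3.1.1 | Rules agree? |
|---|---|---|---|---|
| Does not interfere with activity | No grade, because Grade 1 starts at 2.5 cm | Exempt | Nothing to record | Yes |
| Interferes with activity | Grade 2, by function alone | Exempt | Record | No |
| Prevents daily activity | Grade 3, by function alone | Exempt | Record | No |

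The second and third rows rest on the word *or* in the Grade 2 and Grade 3 cells. It makes the functional limb sufficient without the size limb. Grade 1 instead joins the two limbs with *and*. Note b confirms that function is meant to count.

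The exemption limit of 2.5 cm equals the smallest diameter in Grade 1. This suggests that the sentence in Section 13.2.1 was meant to leave out reactions too small to be graded. It does that in the first row and goes further in the other two.

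The next question is whether the plan recovers the omitted swelling elsewhere. The 7-day diary (Protocol Sections 8.2 and 9.2) collects local reactions, so the raw information exists. SAP Section 8, however, plans analyses of AEs, deaths and SAEs, hematology, vital signs and physical examinations, and none of the diary. No planned table would restore the swelling or its grade.

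Last, the rules were checked again with the exemption confined to reactions under 2.5 cm that meet no Appendix 4 grade. The first row stays exempt, the second and third become reportable, and the three places agree.

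**The case against.** The strongest reply is that Section 13.2.1 is the specific rule on what counts as an AE here, while Section 13.3.1.1 only says how AEs are graded and recorded. On that reading an exempt swelling is not an AE, Section 13.3.1.1 never reaches it, and all sites would handle it alike. This is a fair way to read the two sections together, and variation between sites is then conjecture. It does not remove the mismatch with Appendix 4. A reaction that the protocol's own scale calls Grade 2 or 3 would still be left out, only uniformly.

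A second reply is that the functional limitation has another way into the data. Pain is a solicited local reaction with no size exemption, and Appendix 4 grades it on nearly the same functional wording at Grades 2 and 3. A small swelling that stops someone's activity may well do so through pain, and that pain would be reported. This stands and narrows the point considerably. What remains lost is the swelling itself and its grade, and the whole event where there is no pain.

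A third reply is that nothing important depends on it. The primary and secondary endpoints in Protocol Sections 3.2 and 3.3 all concern systemic allergic or anaphylactic reactions, and the sample size in Section 14.7 uses no local-reaction rate. This also stands, and it sets the weight of the point.

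**Conclusion.** The inconsistency holds on the plain text, for one narrow case: an induration or swelling under 2.5 cm that interferes with or prevents activity. It is minor. It affects the completeness of AE severity reporting and leaves the primary and secondary endpoints, sample size and power untouched. The conclusion assumes only that the Grade 2 and Grade 3 cells mean what their wording says.

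A reader might infer more, in four ways that the documents do not support.

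- **That redness is affected in the same way.** Appendix 4 grades redness at Grades 1 to 3 by diameter alone, starting at 2.5 cm. For those grades the exemption and the scale match.
- **That a small necrotic lesion would escape the stopping rule in Section 12.5**, "One Grade 4 or higher AE that is at least possibly related to the vaccine". Necrosis and exfoliative dermatitis are not among the solicited local reactions in Section 13.2.2 and are not plainly a swelling of a given diameter. They would enter as unsolicited AEs, and possibly as SAEs under Section 13.2.4.
- **That young children are the most likely to be missed.** Nothing in the documents relates age to the size of a swelling or to its effect on activity.
- **That the number affected can be estimated.** Protocol Section 5.1 gives injection-site swelling in 20.4% at ages 5 to 11, but the children enrolled are 5 to 17. It does not say what size counted as a swelling, what share was under 2.5 cm, what share limited activity, or how often pain accompanied it. Any count would rest on invented inputs.

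**What to change.** In Section 13.2.1, confine the exemption to injection-site redness or swelling that measures less than 2.5 cm **and** meets no grade in Appendix 4. Sections 13.2.1 and 13.3.1.1 and Appendix 4 then agree, and reactions too small and too mild to grade stay exempt as before.

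The cost is one clause, a short note to sites and a few more AE records. No new data collection is needed, because the diary already captures these reactions, and no SAP analysis has to change.

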## B. Tables for Laboratory Abnormalities

Serum a	Mild (Grade 1)	Moderate (Grade 2)	Severe (Grade 3)	Potentially Life Threatening (Grade 4) b
Sodium – hyponatremia mEq/L	132-134	130-131	125-129	<125
Sodium – hypernatremia mEq/L	144-145	146-147	148-150	>150
Potassium – hyperkalemia mEq/L	5.1-5.2	5.3-5.4	5.5-5.6	>5.6
Potassium – hypokalemia mEq/L	3.5-3.6	3.3-3.4	3.1-3.2	<3.1
Glucose – hypoglycemia mg/dL	65-69	55-64	45-54	<45
Glucose – hyperglycemia				Insulin requirements or hyperosmolar coma
Fasting - mg/dL	100-110	111-125	>125	
Random - mg/dL	110-125	126-200	>200	
Blood urea nitrogen mg/dL	23-26	27-31	>31	Requires dialysis
Creatinine mg/dL	1.5-1.7	1.8-2.0	2.1-2.5	>2.5 or requires dialysis
Calcium-hypocalcemia mg/dL	8.0-8.4	7.5-7.9	7.0-7.4	<7.0
Calcium-hypercalcemia mg/dL	10.5-11.0	11.1-11.5	11.6-12.0	>12.0
Magnesium-hypomagnesemia mg/dL	1.3-1.5	1.1-1.2	0.9-1.0	<0.9
Phosphorus – hypophosphatemia mg/dL	2.3-2.5	2.0-2.2	1.6-1.9	<1.6
CPK - mg/dL	1.25-1.5 × ULN	1.6-3.0 × ULN	3.1-10 × ULN	>10 × ULN
Albumin – hypoalbuminemia g/dL	2.8-3.1	2.5-2.7	<2.5	–
Total protein – hypoproteinemia g/dL	5.5-6.0	5.0-5.4	<5.0	–
Alkaline phosphate – increase by factor	1.1-2.0 × ULN	2.1-3.0 × ULN	3.1-10 × ULN	>10 × ULN
Liver function tests – ALT, AST increase by factor	1.1-2.5 × ULN	2.6-5.0 × ULN	5.1-10 × ULN	>10 × ULN
Bilirubin – when accompanied by any increase in liver function test increase by factor	1.1-1.25 × ULN	1.26-1.5 × ULN	1.51-1.75 × ULN	>1.75 × ULN
Bilirubin – when liver function test is normal; increase by factor	1.1-1.5 × ULN	1.6-2.0 × ULN	2.0-3.0 × ULN	>3.0 × ULN
Cholesterol mg/dL	201-210	211-225	>226	–
Pancreatic enzymes – amylase, lipase	1.1-1.5 × ULN	1.6-2.0 × ULN	2.1-5.0 × ULN	>5.0 × ULN

ALT = alanine aminotransferase; AST = aspartate aminotransferase; CPK = creatine phosphokinase; ULN = upper limit of normal.

a The laboratory values provided in the tables serve as guidelines and are dependent upon institutional normal parameters.

Institutional normal reference ranges should be provided to demonstrate that they are appropriate.

b The clinical signs or symptoms associated with laboratory abnormalities might result in characterization of the laboratory abnormalities as Potentially Life Threatening (Grade 4). For example, a low sodium value that falls within a grade 3 parameter

(125-129 mEq/L) should be recorded as a grade 4 hyponatremia event if the subject had a new seizure associated with the low sodium value.

Hematology a	Mild (Grade 1)	Moderate (Grade 2)	Severe (Grade 3)	Potentially Life Threatening (Grade 4)
Hemoglobin (female) – g/dL	11.0-12.0	9.5-10.9	8.0-9.4	<8.0
Hemoglobin (female) change from baseline value	Any decrease – 1.5	1.6-2.0	2.1-5.0	>5.0
Hemoglobin (male) – g/dL	12.5-13.5	10.5-12.4	8.5-10.4	<8.5
Hemoglobin (male) change from baseline value – g/dL	Any decrease – 1.5	1.6-2.0	2.1-5.0	>5.0
WBC increase – cell/mm 	10,800-15,000	15,001-20,000	20,001-25,000	>25,000
WBC decrease – cell/mm 	2,500-3,500	1,500-2,499	1,000-1,499	<1,000
Lymphocytes decrease – cell/mm 	750-1,000	500-749	250-499	<250
Neutrophils decrease – cell/mm 	1,500-2,000	1,000-1,499	500-999	<500
Eosinophils – cell/mm 	650-1,500	1501-5,000	>5,000	Hypereosinophilic
Platelets decrease – cell/mm 	125,000-140,000	100,000-124,000	25,000-99,000	<25,000
PT – increase by factor	1.0-1.10 × ULN	1.11-1.20 × ULN	1.21-1.25 × ULN	>1.25 × ULN
PTT – increase by factor	1.0-1.2 × ULN	1.21-1.4 × ULN	1.41-1.5 × ULN	>1.5 × ULN

PPT = partial thromboplastin time; PT = prothrombin time; ULN = upper limit of normal; WBC = white blood cell.

a The laboratory values provided in the tables serve as guidelines and are dependent upon institutional normal parameters. Institutional normal reference ranges should be provided to demonstrate that they are appropriate.

Urine a	Mild (Grade 1)	Moderate (Grade 2)	Severe (Grade 3)	Potentially Life Threatening (Grade 4)
Protein	Trace	1+	2+	Hospitalization or dialysis
Glucose	Trace	1+	2+	Hospitalization or hyperglycemia
Blood (microscopic) – red blood cells per high power field	1-10	11-50	>50 and/or gross blood	Hospitalization or packed red blood cells transfusion

a The laboratory values provided in the tables serve as guidelines and are dependent upon institutional normal parameters. Institutional normal reference ranges should be provided to demonstrate that they are appropriate.

1. PROTOCOL SYNOPSIS

Title	Systemic Allergic Reactions to SARS-CoV-2 Vaccination
Short Title	SARS Vaccination
Clinical Phase	Phase 2
Number of Sites	Approximately 30 clinical sites in the United States
IND Sponsor/Number	National Institute of Allergy and Infectious Diseases (NIAID) / IND# 27215
Study Objectives	
The study is designed with two principal aims: First, to estimate the proportions of systemic allergic reactions to the Pfizer-BioNTech COVID-19 Vaccine and the Moderna COVID-19 Vaccine in a High-Allergy/Mast Cell Disorder (HA/MCD) population. Second, if the risk in the HA/MCD is demonstrable, to determine whether the proportions are higher in the HA/MCD versus a comparison population.
 
Primary Objectives:
 
 • Assess the proportion of participants with systemic allergic reactions to the Pfizer-BioNTech COVID-19 Vaccine in the HA/MCD and comparison populations • Assess the proportion of participants with systemic allergic reactions to the Moderna COVID-19 Vaccine in the HA/MCD and comparison populations 
Secondary Objectives:
 
 • Assess the proportion of participants with severe (Grade 3 or higher per Consortium for Food Allergy Research (CoFAR) Grading Scale for Systemic Allergic Reactions Version 3.0) systemic allergic reactions to the Pfizer-BioNTech COVID-19 Vaccine in the HA/MCD and comparison populations • Assess the proportion of participants with severe (Grade 3 or higher per CoFAR Grading Scale for Systemic Allergic Reactions Version 3.0) systemic allergic reactions to the Moderna COVID-19 Vaccine in the HA/MCD and comparison populations • Assess the proportion of participants with anaphylactic reactions (Levels 1-3) per Brighton Collaboration Criteria to the Pfizer-BioNTech COVID-19 Vaccine in the HA/MCD and comparison populations • Assess the proportion of participants with anaphylactic reactions (Levels 1-3) per Brighton Collaboration Criteria to the Moderna COVID-19 Vaccine in the HA/MCD and comparison populations • Assess the proportion of participants with systemic allergic reactions to the Pfizer-BioNTech COVID-19 Vaccine in the HA/MCD population by dose

	
 Assess the proportion of participants with systemic allergic reactions to the Moderna COVID-19 Vaccine in the HA/MCD population by dose Assess the proportion of participants with systemic allergic reactions to the Pfizer-BioNTech COVID-19 Vaccine in the HA/MCD after adjusting for placebo Assess the proportion of participants with systemic allergic reactions to the Moderna COVID-19 Vaccine in the HA/MCD after adjusting for placebo Assess the difference in proportions of participants with systemic allergic reactions after the second Pfizer-BioNTech COVID-19 Vaccine dose (not placebo arm) versus the first vaccine dose within the placebo arm in the HA/MCD population Assess the difference in proportion of participants with systemic allergic reactions after the second Moderna COVID-19 Vaccine dose (not placebo arm) versus the first vaccine dose within the placebo arm in the HA/MCD population Assess the difference in proportion of HA/MCD participants with systemic allergic reactions to the Pfizer-BioNTech COVID-19 Vaccine between the adult and child populations (for this analysis, the HA group will not include children who qualified for the study on the basis of uncontrolled asthma) Assess the difference in proportion of HA/MCD participants with systemic allergic reactions to the Moderna COVID-19 Vaccine between the adult and child populations (for this analysis, the HA group will not include children who qualified for the study on the basis of uncontrolled asthma) 
Exploratory Objectives:
 
 Assess the risk of systemic allergic reactions to the Pfizer-BioNTech COVID-19 Vaccine and independently to the Moderna COVID-19 Vaccine in the HA/MCD population by baseline covariates Examine possible mechanisms of systemic allergic reactions to the Pfizer-BioNTech COVID-19 Vaccine and to the Moderna COVID-19 Vaccine Identify genotypes associated with increased risk of systemic allergic reactions to the Pfizer-BioNTech COVID-19 Vaccine and to the Moderna COVID-19 Vaccine
Study Design	
This is a multi-center, randomized, initially blinded, phase 2 trial to assess SARS-CoV-2 vaccination systemic allergic reactions in two populations: one population including individuals with a history of recent, severe allergic reactions (High-Allergy [HA]), poorly controlled allergic asthma, or mast cell disorders (MCDs) and one comparison population without severe allergies or mast cell disorders.
 
Participants enrolled under protocol versions 1.0 - 4.0, were randomized 2:2:1:1 to receive the Pfizer-BioNTech COVID-19 Vaccine, Moderna COVID-19 Vaccine, placebo + Pfizer-BioNTech COVID-19 Vaccine, or placebo + Moderna COVID-19 Vaccine.
 
Participants enrolled under protocol versions 5.0 – 8.0 will be randomized 2:1 to receive the Pfizer-BioNTech COVID-19 vaccine or placebo + Pfizer-BioNTech COVID-19 vaccine. Active vaccine may be changed from Pfizer-BioNTech to Moderna, if enrollment is robust and sustained, Participants randomized to one of the placebo groups will receive placebo

	as a first dose and will receive two doses of their assigned active vaccine at subsequent visits.
Primary Endpoints	
 1. The proportion of participants who experience a systemic allergic reaction (CoFAR Grade 2 and above regardless of tryptase, or CoFAR Grade 1 with elevated tryptase [$1.2 \times \text{baseline} + 2 \text{ ng/ml}$]) within the 90-minute post-vaccination observation period to either dose of the Pfizer-BioNTech COVID-19 Vaccine 2. The proportion of participants who experience a systemic allergic reaction (CoFAR Grade 2 and above regardless of tryptase, or CoFAR Grade 1 with elevated tryptase [$1.2 \times \text{baseline} + 2 \text{ ng/ml}$]) within the 90-minute post-vaccination observation period to either dose of the Moderna COVID-19 Vaccine
Secondary Endpoints	
 1. The proportion of participants who experience a severe (Grade 3 or higher per CoFAR Grading Scale for Systemic Allergic Reactions Version 3.0) systemic allergic reactions within the 90- minute post-vaccination observation period to either dose of each vaccine 2. The proportion of participants who experience an anaphylactic reaction (Levels 1-3) per Brighton Collaboration Criteria within the 90-minute post-vaccination observation period to either dose of each vaccine 3. The proportion of participants who experience a systemic allergic reaction (CoFAR Grade 2 and above regardless of tryptase, or CoFAR Grade 1 with elevated tryptase [$1.2 \times \text{baseline} + 2 \text{ ng/ml}$]) within the 90-minute post-vaccination observation period to the first dose 4. The proportion of participants who experience a systemic allergic reaction (CoFAR Grade 2 and above regardless of tryptase, or CoFAR Grade 1 with elevated tryptase [$1.2 \times \text{baseline} + 2 \text{ ng/ml}$]) within the 90-minute post-vaccination observation period to the second dose conditional on no systemic allergic reaction to the first dose 5. The proportion of participants who experience a systemic allergic reaction (CoFAR Grade 2 and above regardless of tryptase, or CoFAR Grade 1 with elevated tryptase [$1.2 \times \text{baseline} + 2 \text{ ng/ml}$]) within the 90-minute post-vaccination observation period to the first dose after adjusting for placebo administration 6. The proportion of participants who experience a systemic allergic reaction (CoFAR Grade 2 and above) within 48 hours of either dose of each vaccine
Exploratory Endpoints	
 1. The proportion of participants who experience a systemic allergic reaction (CoFAR Grade 2 and above regardless of tryptase, or CoFAR Grade 1 with elevated tryptase [$1.2 \times \text{baseline} + 2 \text{ ng/ml}$]) within the 90-minute post-vaccination observation period to either dose 2. Prevalence of polyethylene glycol (PEG) antibodies in vaccine recipients before each vaccination

	
3. Changes in anti-PEG antibody levels 3-4 weeks after the first vaccine dose4. Changes in biomarkers from pre- to post-vaccination and/or after onset of an allergic reaction (e.g., known mediators of systemic reactions due to mast cell activation, markers of inflammatory response, markers associated with activation of the classical and alternative complement pathways or the kinin system)5. Changes in blood transcriptomics after vaccination, and plasma and urine proteomics from pre- to post-vaccination and/or after onset of an allergic reaction6. Genetic variants identified by whole-genome sequencing (applicable only in protocol versions 1.0 - 4.0)
Accrual Objective	
This study will enroll up to 3400 participants. Approximately 60% of participants will be in the High-Allergy/Mast Cell Disorder (HA/MCD) group, and 40% will be in the comparison group. Enrollment of participants who qualify only on the basis of reactions to multiple unrelated drugs will be limited to approximately 300. Enrollment of the Mast Cell Disorder group is anticipated to be at least 200, and not more than 300 participants.
 
Approximately two-thirds of participants enrolled in each of the 2 groups will be female. Under protocol versions 1.0 - 4.0, participants were randomized 2:2:1:1 to receive either the Pfizer-BioNTech COVID-19 Vaccine, Moderna COVID-19 Vaccine, placebo+ Pfizer-BioNTech COVID-19 Vaccine, or placebo + Moderna COVID-19 Vaccine.
 
Under protocol versions 5.0 – 8.0, the study will only enroll children ages 5 through 17 years on the date of first study vaccination/placebo administration. Enrollment of participants aged 18 or older will be closed. Children will be randomized 2:1 to receive either the Pfizer-BioNTech COVID-19 Vaccine or placebo + Pfizer-BioNTech COVID-19 Vaccine. Active vaccine may be changed from Pfizer-BioNTech to Moderna if enrollment is robust and sustained.
 
Participants randomized to one of the placebo groups will receive placebo as a first dose and will receive two doses of their assigned active vaccine at subsequent visits.

Study Duration	
Participant Vaccination and Follow-up:
 
Participants randomized under protocol versions 1.0 - 4.0: Randomized and vaccinated participants will complete study participation in approximately 29 days if vaccinated with the Pfizer-BioNTech COVID-19 Vaccine, 36 days if vaccinated with the Moderna COVID-19 Vaccine, and 50 or 64 days if administered placebo before receiving two doses of either the Pfizer-BioNTech COVID-19 Vaccine or the Moderna COVID-19 Vaccine, respectively.
 
Participants randomized under protocol versions 5.0 – 8.0: Randomized and vaccinated participants who receive both doses of vaccine will complete study participation in approximately 29 days if vaccinated with the Pfizer-BioNTech COVID-19 Vaccine, 36 days if vaccinated with the Moderna COVID-19 Vaccine, and 36 or 43 days if administered placebo before receiving two doses of either the Pfizer-BioNTech COVID-19 Vaccine or the Moderna COVID-19 Vaccine, respectively.

Treatment Description	Each participant will receive 2 doses of either the Pfizer-BioNTech COVID-19 Vaccine or the Moderna COVID-19 Vaccine. Participants randomized to placebo, will receive a placebo dose before receiving 2 doses of either the Pfizer-BioNTech COVID-19 Vaccine or the Moderna COVID-19 Vaccine.
Inclusion Criteria	
Note criteria apply to all cohorts and protocol versions, unless otherwise stated.
 
Individuals who meet all of the following criteria are eligible for enrollment as study participants:
 
Both groups:
 
 1. Participant and/or parent/legal guardian must be able to understand and provide informed consent and/or assent, as applicable 2. Male or non-pregnant female 12 years of age or older on the date of first study vaccination/placebo administration (protocol versions 1.0 - 4.0) OR male or non-pregnant female 5 to 17 years of age on the date of first study vaccination/placebo administration (protocol versions 5.0 – 8.0) 3. Females of childbearing potential must have a negative pregnancy test prior to the first vaccination and placebo administration, if applicable. If a participant becomes pregnant after receiving a placebo dose but prior to receiving study vaccination, she will be discontinued from the study. 4. Females of reproductive potential* and sexually active must agree to use Food and Drug Administration (FDA) approved methods of birth control for the duration of the study. These include hormonal contraceptives, intrauterine device, double barrier contraception (i.e., condom plus diaphragm), or male partner with documented vasectomy. 
*Menopause is defined as at least 12 consecutive months without menses; if in question, a follicle stimulating hormone of ≥ 25 U/mL must be documented.
 
Hysterectomy, bilateral oophorectomy, or bilateral tubal ligation must be documented, as applicable; if documented, women with these conditions are not required to use additional contraception.
 
High-Allergy and Mast Cell Disorder (HA/MCD) group:
 
Individuals who meet at least one of the following criteria are eligible for enrollment in the HA/MCD group:
 
 1. History of a severe allergic reaction to food(s), allergen immunotherapy, insect venom(s), or latex with use of epinephrine within the last 15 years 2. History of an Emergency Department visit with convincing evidence of a systemic allergic reaction (consistent with CoFAR Grade 3 or higher) to food(s), allergen immunotherapy, insect venom(s) or latex within the last 15 years 3. History of documented, immediate allergic reactions to 2 or more unrelated drugs within the last 15 years

	
4. A convincing clinical history, or a history that is accompanied by a positive skin test, of an immediate reaction to a drug, vaccine, or latex within the last 15 years
 
5. History of physician-diagnosed idiopathic anaphylaxis requiring epinephrine, or an Emergency Department visit in the last 15 years
 
6. History of a physician-diagnosed mast cell disorder (e.g., mastocytosis, mast cell activation syndrome (MCAS), or hereditary alpha-tryptasemia). MCAS must meet consensus criteria as defined below:
 
 Criterion A: Typical clinical signs of severe, recurrent (episodic) systemic Mast Cell Activation are present (often in form of anaphylaxis) (definition of systemic: involving at least 2 organ systems) Criterion B: Involvement of Mast Cell (MC) is documented by biochemical studies: preferred marker: increase in serum tryptase level from the individual's baseline to plus 20% + 2 ng/ml Criterion C: Response of symptoms to therapy with MC-stabilizing agents, drugs directed against MC mediator production or drugs blocking mediator release or effects of MC-derived mediators 
All 3 MCAS criteria (A + B + C) must be fulfilled to call a condition MCAS.
 
7. Poorly controlled allergic asthma as evidenced by one hospitalization or one or more systemic (oral or injectable) steroid burst(s) in the 24 months prior to enrollment and evidence of aeroallergen sensitization by blood work, skin test, or appropriate history.
 
8. A doctor diagnosis of food allergy with a convincing clinical history and a positive skin test or positive food challenge, with evidence of reactivity within the last 10 years.
 
Comparison group:
 
Individuals who meet all of the following criteria are eligible for enrollment in the comparison group:
 
 1. No history of allergic asthma or atopic dermatitis within the last 10 years 2. No history of chronic spontaneous urticaria, or angioedema 3. No history of allergic reactions to foods or insect venoms 4. No history of allergic reactions to drugs or vaccines 5. No history of anaphylaxis 6. No history of a mast cell disorder (e.g., mastocytosis, MCAS, or hereditary alpha-tryptasemia)
Exclusion Criteria	
Individuals who meet any of these criteria are not eligible for enrollment as study participants:
 
 1. Inability or unwillingness of a participant and/or parent/legal guardian to give written informed consent and/or assent, as applicable, or comply with study protocol 2. Weight less than 15 kg 3. Prior receipt of any doses of the Pfizer-BioNTech COVID-19 Vaccine, Moderna COVID-19 Vaccine, or any other COVID-19 vaccine

4. History of a severe reaction to any component of the Pfizer-BioNTech COVID-19 Vaccine or Moderna COVID-19 Vaccine
5. History of contact dermatitis with confirmed patch test reaction to PEG
6. History of reaction to Doxil
7. Known exposure to SARS-CoV-2 and still within the quarantine window
8. Symptoms consistent with acute COVID-19 infection or known COVID-19 infection (positive PCR or antigen test) and still within the quarantine window
9. Have an acute illness, including body temperature greater than 100.4°F, within 14 days of the first study vaccination/placebo administration or 3 days prior to each subsequent vaccination
10. History of autoimmune or other disorders requiring systemic immune modulators
11. History of acute urticaria within 28 days of randomization
12. Pregnant
13. Have received any vaccines within 14 days of the first study vaccination/placebo administration or plan to receive other vaccines during the study period
14. Had any allergen immunotherapy administration within 24 hours prior to vaccination/placebo administration or plan to receive within 24 hours after vaccination/placebo administration
15. Have received a biologic therapy within 6 months of randomization
16. Use of systemic steroids for any reason within 28 days of randomization
17. Use of Zileuton within 14 days of randomization
18. Use of any antibody agent for treatment or prevention of COVID-19 within 3 months of randomization
19. Coronary artery disease, peripheral or cerebral vascular disease, unstable angina, or cardiac arrhythmia other than supraventricular tachycardia (SVT)
20. Medically unstable hypertension
21. Current use of beta-blockers, angiotensin-converting-enzyme (ACE) inhibitors, monoamine oxidase (MAO) inhibitors, tricyclic anti-depressants or other agents that could interfere with the treatment of anaphylaxis, in the opinion of the investigator
